13.1 Withdrawal

Participants have the right to withdraw consent for participation in any aspect of the trial at any time. The participants care will not be affected at any time by declining to participate or withdrawing from the trial. In addition, a participant may be withdrawn by the investigator or the Sponsor if enrolment into the trial is inappropriate, the trial plan is violated, or for administrative and/or other safety reasons.

Under these circumstances, a participant may withdraw or be withdrawn from the trial for the following reasons:

- Withdrawal of consent by the participant
- Any alteration in the participants condition which justifies the discontinuation of participation in the Investigator's opinion
- Non-compliance

If a participant initially consents but subsequently withdraws from the trial, clear distinction must be made as to what aspect of the trial the participant is withdrawing from. For the purposes of this trial, these are:

- 1. Withdrawal from questionnaires
- 2. Withdrawal of use of participant contact data (personal identifying data collected for the purposes of contacting participants)
- 3. Withdrawal from future data linkage
- 4. Withdrawal from having research wound swabs taken
- 5. Withdrawal from all aspects of the trial (participant fully withdrawn)

The withdrawal of participant consent shall not affect the trial activities already carried out and the use of data collected prior to participant withdrawal. The use of the data collected prior to withdrawal of consent is based on informed consent before its withdrawal. Participants will be informed of this before they join the

trial as outlined in the PIS. All data collected prior to participant withdrawal will be kept with the other trial data and archived after the trial analysis.

Furthermore, it is important to collect safety data ongoing at the time of withdrawal, especially if the participant withdraws because of a safety event.

In the event of a withdrawal from all aspects of the trial, any unprocessed samples at the central laboratory must be disposed.

The withdrawal CRF should be completed on the participant's behalf by the researcher/ clinician based on information provided by the participant. This withdrawal CRF should be recorded in the Excise trial database.

Any queries relating to potential withdrawal of a participant should be forwarded to the trial email inbox ([contact]).

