Once potential interview participants have had time to consider the study information, potential interview participants will be asked by a delegated member of the research team tick the qualitative statement on the informed consent form or complete a consent to contact form as appropriate for trial participants or HCPs. For those that opt to consent to participate in an interview, the Qualitative researcher (QR) will be notified and participant details reviewed for sampling (site, age, gender, trial arm, surgical site). Those then sampled for interview will be contacted by the QR and sent the PIS for interviews, along with a consent form, elicitation

guidance document, diary booklet, timeline example and stamped addressed envelope. Once potential participants have had time to consider the study information the QR will contact them to discuss consent and arrange a suitable time for an interview.

Patients who are eligible for trial participation but decline to participate may opt to consent to participate in qualitative interviews. Health professionals involved in the trial may consent to participate in qualitative interviews.

After the participant has entered the trial, the investigator must remain free to give alternative treatment to that specified in the protocol, at any stage, if they feel it to be in the best interest of the participant. However, the reason for doing so should be recorded and the participant will remain within the trial for the purpose of follow up and data analysis according to the treatment option to which they were allocated. Similarly, the participant must remain free to withdraw at any time from the protocol treatment without giving reasons and without prejudicing their further treatment (see Section 13.1 or further details on Withdrawal).

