13.2 Lost to follow up

Participants will be identified as lost to follow-up if the research team is unable to complete the follow up at day 30 following surgery. Measures that we will take to try and get the missing information include three attempts to telephone or text the participants or the participant's support person if the participant has elected to nominate one. If we are unable to contact the participant by telephone, we will also send them a letter asking them to contact the trial centre, if the participant has agreed to provide their address. Where participants are lost to follow up or withdraw before day 30, SSI outcome data will be censored at the date of last known follow-up assessment/clinic visit/participant contact before day 30.

For avoidance of doubt, in respect to sample collection, If the participant is lost to follow up, then they are not subject to the withdrawal processes, and the original consent stands.

14 Pharmacovigilance

The PI at each site is responsible for ensuring that all site staff involved in this trial are familiar with the content of this section.

All Serious Adverse Events (SAEs) must be reported immediately (and within 24 hours of knowledge of the event) by the PI at the participating site to the CTR PV and Safety Specialist.

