15.7 Inclusion in analysis

This analysis will include all randomised participants regardless of intervention receipt (as we will be using a treatment policy strategy for handling this intercurrent events).

16 Analysis

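### Section 13.1 permits withdrawal from the trial for non-compliance or plan violation, and 13.2 then censors SSI data, against the all-randomised, treatment-policy analysis

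*Protocol*

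**What the plan says.** Section 13.1 gives two sets of grounds. First, "a participant may be withdrawn by the investigator or the Sponsor if enrolment into the trial is inappropriate, the trial plan is violated". The same sentence adds administrative and safety grounds. Second, "a participant may withdraw or be withdrawn from the trial for the following reasons": withdrawn consent, a change in the participant's condition that in the investigator's opinion justifies stopping, and "Non-compliance".

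The section has five withdrawal levels: questionnaires, contact data, future data linkage, research swabs, and full withdrawal. None of them covers a participant who missed the trial treatment but stays in follow-up. On data, "All data collected prior to participant withdrawal will be kept with the other trial data", and safety data ongoing at withdrawal are to be collected. The section does not say that SSI assessment continues.

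Section 13.2: "Where participants are lost to follow up or withdraw before day 30, SSI outcome data will be censored" at the last contact before day 30.

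Three sections point the other way:
- Section 15.7: "This analysis will include all randomised participants regardless of intervention receipt", under a treatment-policy strategy. Section 16.1 repeats this for a logistic regression on SSI within 30 days of randomisation.
- Section 9.4: if the investigator gives a treatment other than the one specified, "the participant will remain within the trial for the purpose of follow up and data analysis", as allocated. It also recognises withdrawal from protocol treatment as something separate.

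**The concern.** A treatment-policy strategy works only if outcomes are collected after the intercurrent event. Non-receipt of the capsules is the intercurrent event that 15.7 names, yet under 13.1 it can be a reason for removal from the trial. Two sites could handle the same missed dose in opposite ways, and each could cite the protocol.

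The trial drug is a single dose given before surgery. Once surgery is done, a site has no remaining trial treatment to stop, so full withdrawal for non-compliance achieves little beyond ending follow-up. Late-found ineligibility is also plausible: one exclusion concerns wounds left for delayed reconstruction or secondary-intention healing, which may become clear only at operation, after randomisation.

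At stake is avoidable post-randomisation loss of the primary outcome, related to non-receipt. The result would be labelled treatment policy but would lie nearer to the effect in recipients. A logistic model for a binary outcome has no direct use for a censoring time. Multiple imputation, which 16.1 gives as an example, is a poor substitute for an outcome that a scheduled call could have recorded.

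**Working it through.** **The same event under each set of rules**

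| Event after randomisation | Under 9.4, 15.7, 16.1 | Under 13.1 and 13.2 |
|---|---|---|
| Capsules not taken | In the analysis regardless of receipt | May be withdrawn; SSI data censored |
| Other treatment given by the investigator | Stays for follow-up and analysis | May be withdrawn if read as a plan violation; SSI data censored |
| Found ineligible | All randomised are analysed | May be withdrawn as inappropriately enrolled; SSI data censored |

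**Inputs.** From section 15.3: SSI 30% on placebo, a 15-point difference (so 15% on flucloxacillin), two-sided alpha 0.05, power 90%, 15% loss, 190 per arm. Assumed: non-receipt k of 2%, 5% or 10% in each arm; non-recipients in the flucloxacillin arm carry the 30% risk; all of them are fully withdrawn before any SSI is recorded.

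**Step 1: the plan's own figure.** With pooled proportion 0.225,
n = [1.960 × √(2 × 0.225 × 0.775) + 1.282 × √(0.30 × 0.70 + 0.15 × 0.85)]² / 0.15² = (1.1575 + 0.7445)² / 0.0225 = 160.8, so 161 per arm.
161 / 0.85 = 189.4, so 190 per arm and 380 in total. The stated figure reproduces.

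**Step 2: shift in the estimate if the drug works.** The treatment-policy risk on flucloxacillin is 0.15(1 − k) + 0.30k.

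| k | Risk on flucloxacillin | Treatment-policy difference | Difference after removal | Gap |
|---|---|---|---|---|
| 2% | 15.3% | 14.7 | 15.0 | 0.3 |
| 5% | 15.75% | 14.25 | 15.0 | 0.75 |
| 10% | 16.5% | 13.5 | 15.0 | 1.5 |

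Section 16.1 reports odds ratios. On that scale (unadjusted), removal gives (0.15/0.85)/(0.30/0.70) = 0.41. The treatment-policy value is (0.1575/0.8425)/(0.30/0.70) = 0.44 at 5% and (0.165/0.835)/(0.30/0.70) = 0.46 at 10%.

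**Step 3: shift if the drug does nothing.** Blinded removal should take the same share, at the same risk, from both arms. With 30% in each arm before and after, the difference stays at zero.

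**Step 4: power with the difference held at 15 points.** For m analysable per arm, power = Φ[(0.15√m − 1.1575) / √0.3375].
- Planned: 190 × 0.85 = 161.5 gives 90.1%.
- Loss taken from the analysable group: 161.5 × 0.95 = 153.4 gives 88.6%; 161.5 × 0.90 = 145.4 gives 86.9%.
- Loss added to the planned 15%: 190 × 0.80 = 152 gives 88.3%; 190 × 0.75 = 142.5 gives 86.2%.

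**Step 5: does keeping everyone raise power?** Under the same assumptions, no. With 161.5 per arm followed and the diluted differences of 14.25 and 13.5 points, power is 86.5% and 82.2%. The higher figures in step 4 belong to the effect in recipients, which is a different estimand. The argument for continued follow-up therefore rests on the estimand rather than on power.

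**The case against.** The case on the other side is substantial.

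- **The clause is discretionary.** A reader might infer that the protocol creates missing outcomes by rule. It does not: 13.1 says a participant may be withdrawn, and sends queries about potential withdrawals to the central trial team. This stands.
- **Not every withdrawal ends SSI assessment.** Withdrawal from questionnaires, data linkage or research swabs does not by its terms stop it, and withdrawal of contact data may only hinder it. SSIs recorded before withdrawal are kept. This stands; the problem lies with full withdrawal.
- **Other sections support retention.** Section 9.4 separates withdrawal from protocol treatment, 16.1 plans to describe non-adherence, and section 19 already has deviations documented. These show the intent, but none of them overrides 13.1 or 13.2.
- **Bias.** A reader might infer that the clause biases the trial towards benefit in general, or could produce a false positive. The documents do not support that. The trial is double-blind, so removal for non-receipt should not depend on arm. The estimate is exaggerated only if there is a real effect.
- **Frequency.** A reader might take 5-10% as an expected rate. The protocol gives no rate. Eligibility is confirmed before randomisation (9.2) and site staff confirm receipt of the dose (10.10), so the true rate may well be lower. Such losses might also fall within the planned 15%.

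**Conclusion.** The conflict is real and touches the primary outcome, but its expected numerical effect is small. Sections 13.1 and 13.2 together permit, without requiring, loss of 30-day SSI status for participants whom 15.7 and 16.1 need and whom 9.4 would keep. The plan states this rule; it is not a detail left to the SAP.

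If flucloxacillin works as assumed, full withdrawal of non-recipients overstates the treatment-policy difference by 0.75 points at 5% non-receipt and 1.5 points at 10%. The planned 90% power falls by about 1 to 4 percentage points with the difference held at 15 points. All of this rests on an assumed rate, on non-recipients carrying the placebo risk, and on full withdrawal before any SSI is recorded. With no drug effect and intact blinding, no difference is created. The reason to act is that uncollected 30-day outcomes cannot be recovered at analysis and the correction is cheap.

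**What to change.** Reconcile 9.4, 13.1, 13.2, 15.7 and 16.1:

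1. In 13.1, state that non-receipt of the IMP, a protocol deviation, or ineligibility found after randomisation is recorded as a deviation, as section 19 already provides. State that it does not by itself end the scheduled SSI, safety and EQ-5D-5L follow-up.
2. Make this subject to withdrawal of consent, safety decisions and section 9.4.1. The last exception is needed because 9.4.1 requires full withdrawal in some capacity situations where nobody has withdrawn consent.
3. Remove non-compliance and violation of the trial plan as stand-alone grounds for ending follow-up. The safety grounds and the participant's right to withdraw stay as they are.
4. Add a withdrawal-CRF level along the lines of: trial treatment not received, follow-up continues.

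The cost is a wording amendment, one CRF option, and a few telephone contacts that are already in the schedule. The sample size of 380 does not change. It should be done while participants are still being followed.

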13.2 Lost to follow up

Participants will be identified as lost to follow-up if the research team is unable to complete the follow up at day 30 following surgery. Measures that we will take to try and get the missing information include three attempts to telephone or text the participants or the participant's support person if the participant has elected to nominate one. If we are unable to contact the participant by telephone, we will also send them a letter asking them to contact the trial centre, if the participant has agreed to provide their address. Where participants are lost to follow up or withdraw before day 30, SSI outcome data will be censored at the date of last known follow-up assessment/clinic visit/participant contact before day 30.

For avoidance of doubt, in respect to sample collection, If the participant is lost to follow up, then they are not subject to the withdrawal processes, and the original consent stands.

14 Pharmacovigilance

The PI at each site is responsible for ensuring that all site staff involved in this trial are familiar with the content of this section.

All Serious Adverse Events (SAEs) must be reported immediately (and within 24 hours of knowledge of the event) by the PI at the participating site to the CTR PV and Safety Specialist.

14.1 Definitions

Table 3: Definitions of Adverse and Serious Adverse Events and Reactions.

Term	Definition

Adverse Event (AE) Adverse Reaction (AR)	Any untoward medical occurrence in a participant or clinical trial participant administered a medicinal product and which are not necessarily caused by or related to that product. Any untoward and unintended response in a clinical trial participant to an investigational medicinal product which is related to any dose administered to that participant.					
Serious Adverse Event (SAE)	 Any adverse event that - Results in death Is life-threatening* Required hospitalisation or prolongation of existing hospitalisation** Results in persistent or significant disability or incapacity Consists of a congenital anomaly or birth defect Other medically important condition*** 					
Serious Adverse Reactions (SARs)	Any SAE occurring in a clinical trial participant for which there is a reasonable possibility that it is related to the IMP at any dose administered.					
Suspected Unexpected Serious Adverse Reactions (SUSARs)	A SAR, the nature and severity of which is not consistent with the Reference Safety Information (RSI) for the IMP.					

^{*}Note: The term 'life-threatening' in the definition of serious refers to an event in which the trial participant was at risk of death at the time of the event or it is suspected that used or continued used of the product would result in the subjects death; it does not refer to an event which hypothetically might have caused death if it were more severe.

[figure not shown]
14.2 Trial Specific SAE Reporting requirements

There are no additional SAE reporting requirements in the trial.

Pre-existing conditions should only be reported if they met the definitions for an SAE and if the condition worsens by at least one CTCAE grade.

^{**} **Note:** Hospitalisation is defined as an inpatient admission, regardless of the length of stay, even if the hospitalisation is a precautionary measure for continued observation. Pre-planned hospitalisation e.g. for pre-existing conditions which have not worsened, or elective procedures, does not constitute an SAE.

^{***} Note: other events that may not result in death, are not life-threatening, or do not require hospitalisation, may be considered as an SAE when, based upon appropriate medical judgement, the event may jeopardise the participant and may require medical or surgical intervention to prevent one of the outcomes listed above.

14.3 Causality

Causal relationship of SAEs and SARs in this trial will be assessed for the following:

Table 4. Causal relationship assessment of adverse events

IMP: Oral flucloxacillin
nIMPs: N/A
Procedures: N/A

The PI (or another delegated medically qualified doctor from the trial team) and Clinical co-Chief Investigator (or another medically qualified doctor from the Trial Management Group) will assess each SAE to determine the causal relationship according to the following categories:

Table 5: Definition of causal relationship with IMP.

Relationship	Description	Reasonable possibility
		that the SAE may have
		been caused by the IMP?
Unrelated	There is no evidence of any causal relationship with the trial/intervention.	No
Unlikely	There is little evidence to suggest there is a causal relationship with the trial/intervention (e.g. the event did not occur within a reasonable time after administration of the trial medication). There is another reasonable explanation for the event (e.g. the participant's clinical condition, other concomitant treatment).	No
Possible	There is some evidence to suggest a causal relationship with the trial/intervention (e.g. because the event occurs within a reasonable time after administration of the trial medication). However, the influence of other factors may have contributed to the event (e.g. the participant's clinical condition, other concomitant treatments).	Yes
Probable	There is evidence to suggest a causal relationship and the influence of other factors is unlikely.	Yes
Definite	There is clear evidence to suggest a causal relationship and other possible contributing factors can be ruled out.	Yes

The causality assessment given by the Principal Investigator (or delegate) cannot be downgraded by the clinical co-Chief Investigator (or delegate), and in the case of disagreement both opinions will be provided.

14.4 Expectedness

The clinical co-Chief Investigator (or another delegated appropriately qualified individual) will assess each SAR to perform the assessment of expectedness.

The expectedness assessment should be made with reference to the current Reference Safety Information (RSI) for each IMP. Expectedness decisions must be based purely on whether the event is listed in the RSI; other factors such as the participant population and participant history should not be taken into account. Expectedness is not related to what is an anticipated event within a particular disease. SARs which add significant information on specificity or severity of a known, already documented adverse event constitute unexpected events. Fatal and life-threatening (LT) SARs should not be considered expected (unless explicitly stated in the RSI and approved by the NCA). For example, an event more specific or more severe than that described in the RSI is considered unexpected.

IRAS: 1009425

Table 6 below lists the RSI that should be referenced:

Table 6. Reference Safety Information

IMP	RSI to be used for	Relevant section to be used for	
	expectedness assessment	expectedness assessment	
Oral flucloxacillin	SmPC for Flucloxacillin	Section 4.8 of SmPC	
	Capsules 500 mg to be used as		
	RSI		

Reference Safety Information (RSI) on any CTR trial will be reviewed regularly according to CTR procedures.

14.5 Reporting procedures

14.5.1 Participating Site Responsibilities

The PI (or delegated medically qualified doctor from the trial team) should sign and date the SAE CRF to acknowledge that he/she has performed the seriousness and causality assessments. Investigators should also report SAEs to their own health boards or trust in accordance with local practice.

A completed SAE form for all events requiring immediate reporting should be submitted via fax or email to the CTR within 24 hours of knowledge of the event. A separate form must be used to report each event, irrespective of whether or not the events had the same date of onset.

The participant will be identified only by trial number, month, and year of birth and initials. The participant's name (or any other personal identifiers) should not be used on any correspondence.

It is also required that sites respond to and clarify any queries raised on any reported SAEs and report any additional information as and when it becomes available through to the resolution of the event. Additionally, CTR/ pharmaceutical companies may request additional information relating to any SAEs/ SARs and the site should provide as much information as is available to them in order to resolve these queries.

Serious Adverse Event (SAE) email address:

[contact]

SAE [contact]

SAEs should be reported from time of randomisation, and up to, and including 30 days after the participant receives their dose of the IMP. SARs (such as long-term side effects of trial treatment under investigation) should continue to be reported until the end of follow up as defined in the protocol.

SAEs should be graded using the NCI Common Terminology Criteria for Adverse Events (CTCAE) Version 5.0.

IRAS: 1009425

An SAE form should contain at least the minimum information:

• Full participant trial number.

- An Adverse Event / Adverse Reaction.
- Trial intervention.
- A completed assessment of the seriousness, and causality as performed by the PI (or another appropriately medically qualified doctor registered on the delegation log).

If any of these details are missing, the site will be contacted, and the information must be provided by the site to the CTR within 24 hours.

Except SSIs, no other AEs should be reported on the CRF as Flucloxacillin is a marketed product with a significant amount of safety data available.

